### 3.3.3 Study Parameters

The selected study parameters are appropriate to verify the clinical efficacy of Panzyga in PANS. With the exception of MINI-KID, all scales will be completed electronically, and sites are requested to use electronic questionnaires to reduce variability across patients and to ensure critical consistency of measurements. All assessments except CY-BOCS can be carried out by the treating physician, to prevent unblinding. A strategic central reader system has been established that serves as an independent expert panel to standardize reliability on the study's primary outcome measure (CY-BOCS). Standardization will also include a training program to ensure that all raters from different sites are reliable and remain so throughout the trial. To overcome rater variability as far as possible, the CY-BOCS rater should remain the same person. For the clinical interview scales CY-BOCS, CGI-S/I, and MINI-KID, the rater should meet the following credentials: MD/DO with Board Certification or Board Eligible in Child/Adolescent Psychiatry or related discipline; MD/DO with Board Certification or Board Eligible in Neurology/ Immunology/ Neuroimmunology; or PhD/PsyD with a degree in clinical psychology or related discipline. The clinical raters should also have significant clinical experience with psychiatric interviews and working with children with PANS. Whenever possible, raters should remain the same throughout the study for individual subjects.

The **CY-BOCS** scale score is a clinician-rated, semi-structured interview for rating the presence or absence, as well as the severity of obsessive-compulsive symptoms. Considerable data support the reliability and validity of both the adult [42, 43] and child versions of this scale [44]. The CY-BOCS yields a total obsession score, a total compulsion score and combined total score (maximum total CY-BOCS score=40). If in-person administration is not possible, the interview may be carried out via video conference (Zoom, WebEx etc.), but telephone administration without video is not permitted.

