## 5.6 Blinding and Breaking the Study Blind

Study personnel blinded to treatment assignment will not have access to unblinded information until the study is formally unblinded.

The investigators will be provided with an unblinding procedure to disclose the actual treatment of a particular patient in case of medical emergency; this will be done through the IRT system.

To maintain blinding, infusions will be given in blinded infusion bags (corresponding to a volume of 2 g/kg BW Panzyga per cycle or placebo at each infusion day as tolerated by the patient, or by investigator's discretion).

The infusion bag is then blinded with a non-transparent over-pouch. The non-transparent over-pouch will be put over the infusion bag to maintain blinding. Both containers (infusion bag and over-pouch) will be re-labeled with a blinding label. The blinding label will be stuck on by the unblinded hospital pharmacist or designee.

The blinding labels will be identical for both Panzyga and placebo, so that the content of the bags is only known to the unblinded hospital pharmacist or designee. The unblinded hospital pharmacist or designee will send the infusion bag(s) per patient (potentially already fixed to the non-transparent infusion line) to the ward.

Infusion bags, over-pouches, labels, and non-transparent infusion lines/transparent lines with sleeves will be provided to the site.

To further ensure the blinded character of the study, the investigator or designee who applies the medication to the patient will not be involved in any other study procedures other than drawing blood samples or checking for vital signs, i.e. will not be involved in any patient ratings

or AE assessments. In an effort to protect the blinding of key efficacy ratings, the independent evaluator who completes clinician efficacy ratings (CY-BOCS) will not have knowledge of or access to adverse event reports.

The patient will be blinded with respect to study treatment throughout the study.

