#### 7.1.4 Laboratory parameters

## 7.2 Efficacy Assessments

### 7.2.1 Assessments for Primary Efficacy Endpoint(s)

To study improvement of neuropsychiatric symptomatology and behavior in PANS/PANDAS patients, mean changes in the total CY-BOCS score from Baseline to Week 9 will be compared between Panzyga and placebo treatment to demonstrate superiority. The following measurement scores on obsessive-compulsive symptoms will be recorded in investigator-led interviews:

As described in Section 3.3.3, the CY-BOCS yields a total obsession score, a total compulsion score and combined total score (maximum total CY-BOCS score = 40).

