#### 7.5 Appropriateness of Measurements

The measurements selected in this study are appropriate to verify the superior clinical efficacy of Panzyga vs placebo and the efficacy of Panzyga to improve psychiatric symptoms. The selected endpoints for this study rely on validated tools and study parameters that have been used in this study population (see Section 3.3.3).

- Considerable data support the reliability and validity of the pediatric version of the CY-BOCS scale
- The CGI rating scales are commonly used measures of symptom severity, treatment response and the efficacy of treatments in clinical trials of patients with mental disorders

- The COIS-R is a specific and commonly used measure of OCD-related impairment [46, 47].
- The PTQ is widely used, correlates highly with the YGTSS, and is supported by use in intervention trials [49].
- The SNAP-IV Parent scale has been used in children and has served as a primary outcome measure in a number of medication trials
- The C-SSRS interview has been validated in pediatric patients [55, 60] and has been used as a primary outcome in several pediatric clinical trials [61, 62].

All assessments except CY-BOCS can be carried out by the treating investigator, to prevent unblinding. A strategic central reader system has been established that serves as an independent expert panel to standardize reliability on the study's primary outcome measure (CY-BOCS). Standardization will also include a training program to ensure that all raters from different sites are reliable and remain so throughout the trial. To overcome rater variability as far as possible, the CY-BOCS rater should remain the same person. For the clinical interview scales CY-BOCS and MINI-KID, the rater should meet the following credentials: MD/DO with Board Certification or Board Eligible in Child/Adolescent Psychiatry or related discipline or PhD/PsyD with a degree in clinical psychology or related discipline. The clinical raters should also have significant clinical experience with psychiatric interviews and working with children with PANS and should remain the same throughout the study.

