## 8.6 Independent Data Monitoring

### 8.6.1 Strategic Central Reader System

A team of expert advisors, who are clinical psychologists or neuropsychologists with extensive experience (e.g. clinical experience with individuals with neuropsychiatric disorders) and expertise in the administration and scoring of the test will be deployed by the Sponsor. This deployment will allow ongoing feedback on errant administration and scoring practices. The feedback may include recommendations on how to address scoring errors, reminders of best practices, and—in the worst cases—recommendation that the rater receive remedial training. The following central monitoring modalities will be applied:

- Source document review
- Review of audio recordings that are obtained during the CY-BOCS interviews

This central reader process serves to minimize errors over time and increase assessment accuracy and data quality.

The members of the central reader system must not actively recruit patients.

The central reader process will be developed before study start to serve as the central reference document for this procedure.

In addition to the central reader system described above, a central rating panel will be introduced for sites that are unable to provide qualified experts for rating the CY-BOCS and MINI-KID scales.

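### The protocol is inconsistent about who rates the CY-BOCS, and the rater's shield in Section 5.6 names only adverse event reports

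*Protocol*

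**What the plan says.** Five places in the protocol bear on who scores the CY-BOCS.

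- **Section 7.2.1**, which specifies the primary assessment, says the scores "will be recorded in investigator-led interviews".
- **Section 5.6**, on blinding, says that "the independent evaluator who completes clinician efficacy ratings (CY-BOCS) will not have knowledge of or access to adverse event reports". It also bars the person who gives the infusion from any rating.
- **Section 3.3.3** says "All assessments except CY-BOCS can be carried out by the treating physician, to prevent unblinding". For CY-BOCS, CGI-S/I and MINI-KID raters it gives three credential routes, one of which is "MD/DO with Board Certification or Board Eligible in Neurology/ Immunology/ Neuroimmunology".
- **Section 7.5** repeats the separation almost word for word: "All assessments except CY-BOCS can be carried out by the treating investigator, to prevent unblinding". For CY-BOCS and MINI-KID raters it gives only two routes: "MD/DO with Board Certification or Board Eligible in Child/Adolescent Psychiatry or related discipline or PhD/PsyD with a degree in clinical psychology or related discipline".
- **Section 8.6.1** provides central review of CY-BOCS source documents and audio recordings, and adds that "a central rating panel will be introduced for sites that are unable to provide qualified experts for rating the CY-BOCS and MINI-KID scales".

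Both credential paragraphs also ask for substantial experience of psychiatric interviewing and of children with PANS, and both describe a rater training program.

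**The concern.** CY-BOCS is a clinician-rated, semi-structured interview, so protection of the primary comparison depends on what the rater knows. Elsewhere in the protocol the investigator grades adverse events (Section 7.3.2.2) and must have reviewed the latest laboratory results before the next infusion cycle (Section 6). If Section 7.2.1 means that same person, it names someone whom Section 5.6 excludes. A site could follow either section and believe that it complied.

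The shield in Section 5.6 is also narrower than its purpose. High-dose IVIG leaves traces that saline does not, and adverse event reports are only one place where they appear. If a rater can guess the assignment, expectation can enter the Week 9 scores.

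The credential mismatch raises a different issue: two sites could apply different standards to the same rater, and nobody could say afterwards which one was right.

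**Working it through.** No arithmetic applies. The check is to set the passages side by side.

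**Step 1. Who conducts the interview?**

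| Section | Person | Relation to safety data |
|---|---|---|
| 7.2.1 | Investigator leads the interview | Not stated |
| 5.6 | Independent evaluator | No adverse event reports |
| 3.3.3 and 7.5 | Not the treating physician or investigator, by implication | Reason given: to prevent unblinding |
| 7.3.2.2 | Investigator grades adverse events | Full access |
| 6 | Investigators review laboratory results before each cycle | Full access |

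Nobody can both grade adverse events and be kept away from adverse event reports. On the usage of Sections 6 and 7.3.2.2, therefore, 7.2.1 conflicts with 5.6. The two agree only if 7.2.1 uses the word more widely, for any qualified clinician working under the delegation allowed in Section 8.3. The visible text does not say which is meant. Sections 3.3.3 and 7.5 do not settle it outright, because they state what the treating physician can do and leave the CY-BOCS exclusion to inference.

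**Step 2. What does the shield cover?**

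- Adverse event reports: withheld in Section 5.6.
- Coombs test and hemolysis results: not named. Section 7.5 says the direct Coombs test is there to look for passively transferred blood group antibodies, and Section 7.3.5.2 ties these to IVIG.
- IgG concentrations: not named. Section 7.4.1 defines a parameter for the rise in trough levels over the three cycles, which would not be expected with saline.
- Infusion records: not named. Under Section 5.4 the rate is halved or the infusion interrupted when an adverse event occurs, so the record can reveal a reaction.

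Section 5.6 opens by keeping unblinded information from blinded personnel. A Coombs or IgG result is not a treatment code, so whether that sentence reaches it is open.

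**Step 3. Do the credential lists agree?**

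| Route | 3.3.3 | 7.5 |
|---|---|---|
| Physician, child/adolescent psychiatry or a related field | Yes | Yes |
| Physician, neurology, immunology or neuroimmunology | Yes | Not listed |
| Doctorate, clinical psychology or a related field | Yes | Yes |
| Scales covered | CY-BOCS, CGI-S/I, MINI-KID | CY-BOCS, MINI-KID |

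The lists differ. The related-field wording might be read to include neurology, but it is undefined, and Section 3.3.3 uses it and still lists neurology and immunology separately.

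**Step 4. What follows from the mismatch?**

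- The Section 8.6.1 panel is triggered when a site lacks qualified raters. With two definitions, a site staffed only by neurologists or immunologists cannot tell whether it needs the panel.
- Protocol Section 4.5 and SAP Section 7 require deviations to be classified, and important ones remove a patient from the per-protocol set. The status of a neurologist's rating is undetermined.
- MINI-KID confirms the OCD diagnosis in inclusion criterion 2a, so the same doubt reaches eligibility.
- Rater continuity differs too: Section 3.3.3 softens it to whenever possible for individual patients, and Section 7.5 does not.

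**Step 5. What cannot be seen?** The list that should follow the sentence in Section 7.2.1 is missing from the public version. The visit procedures in Section 6.1, the flow charts, and much of the laboratory and IgG handling text are redacted.

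**The case against.** The best reply is that the intention is plain. Sections 3.3.3, 5.6 and 7.5 all separate the CY-BOCS rater from the treating physician, and one adjective in 7.2.1 stands against them. That adjective may only contrast a clinician interview with parent or self report. The word investigator is not used for one fixed person anyway: Section 5.6 bars the investigator or designee who infuses from assessing adverse events, while 7.3.2.2 gives that task to the investigator. No passage hands laboratory results to the evaluator, and rater instructions may sit in the redacted text. On credentials, Section 3.3.3 expressly accepts neurology and immunology, both sections add an experience requirement, and Section 8.6.1 adds central review, feedback and retraining.

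Most of this stands. It shows a wording fault in a design that means to be sound. Two parts do not dispose of the point. Training and audio review address how the interview is given and scored; they do not establish what the rater had seen or which credential list applies. And redacted text could clarify 7.2.1 or the shield, but it leaves the visible difference between 3.3.3 and 7.5 in place.

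A reader might go further and infer that the primary endpoint can be scored by an unqualified or functionally unblinded rater. The documents do not support that. A rater accepted under 3.3.3 is qualified under the protocol's own terms, nothing shows that such raters score less accurately, and an investigator who both treated the patient and rated the CY-BOCS would be acting against three sections.

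**Conclusion.** The point holds as an internal inconsistency about the primary-endpoint rater, with a shield that, in the visible text, covers only one of several sources that could suggest assignment. It changes no sample size, error rate or analysis.

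Its effect on the estimate cannot be quantified. Any bias would be the share of patients rated by an unshielded person multiplied by the shift in their ratings. The documents give neither factor, and the direction would also have to be assumed, so no figure in CY-BOCS points is offered. The case for acting is that the endpoint is subjective and primary, and the correction is nearly free.

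The conclusion on 7.2.1 assumes that investigator carries its usual meaning from Sections 6 and 7.3.2.2. The conclusion on the shield assumes that the redacted procedures do not already withhold these records, which should be checked against the full protocol. The credential mismatch needs neither assumption.

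**What to change.** 1. In Section 7.2.1, replace the reference to investigator-led interviews with interviews led by the independent evaluator defined in Section 5.6.
2. In Section 5.6, extend what is withheld from that evaluator to laboratory results (including hemolysis and Coombs tests), IgG concentrations and infusion records, unless the unredacted procedures already do so.
3. Have the sponsor put one credential list in both 3.3.3 and 7.5. It should say whether neurology and immunology qualify, define related discipline, and state which scales it covers. The rater-continuity wording should be aligned at the same time.

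The documents do not settle which credential list is the intended one. Section 3.3.3 is the fuller text, so 7.5 may be the one out of date, and the choice belongs to the sponsor. Whichever list is kept, current raters should stay with patients already enrolled. The protocol is dated July 2023 for a study planned to start in Q3 2021, and a change of rater part-way through a patient's follow-up would go against the continuity that both sections ask for.

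The cost is minor protocol wording and restricted record access for the evaluator. If the narrower list is chosen, some sites may use the existing central panel more often. No new role is needed.

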## 4 STUDY POPULATION

### 4.1 Population Base

Patients will be aged 6–17 years, with moderate to severe symptoms PANS with prominent and stable OCD symptoms (i.e. CGI—Severity-OCD rating of  $\geq 4$  or higher on 2 ratings without a change of more than 1 unit between measurements). All patients will meet criteria for PANS, including the sudden onset of obsessive-compulsive symptoms and at least two of seven additional associated neuropsychiatric symptoms. It is estimated that a minimum of █ patients will need to be enrolled, to ensure that at least █ patients are evaluable for the primary endpoint. The total number of patients enrolled for the final analysis may change, depending on the outcome of the interim analysis. Patients who drop out or are withdrawn from the study will not be replaced, but enrollment will continue until the total evaluable number of required patients for primary endpoint assessment has been reached.

Enrollment was staggered in the sense that it was paused after the first █ patients had been randomized and enrolled in the study, in order to enable a planned IDMC review of unblinded safety and PK data, including IgG trough levels. Enrollment resumed only after IDMC data review of the first █ patients had been completed, and the IDMC had recommended to continue enrollment in the study.

#### 4.1.1 Inclusion Criteria

Patients who meet all of the following criteria are eligible for the study:

1. Patients  $\geq 6$  to  $\leq 17$  years of age.
2. Confirmed diagnosis of moderate to severe PANS with prominent and stable OCD symptoms (i.e. CGI—Severity-OCD rating of  $\geq 4$  or higher on 2 ratings without a change of more than 1 unit between measurements) based on the following criteria [1]:
  - a. Abrupt dramatic onset of OCD meeting DSM-5 diagnostic criteria for OCD as confirmed by the MINI-KID-7
  - b. Concurrent presence of additional neuropsychiatric symptoms, with similarly severe and acute onset, from at least two of the following seven categories, that are not better explained by a known neurologic or medical disorder, such as SC, systemic lupus erythematosus, Tourette disorder, or other:
    - i. Anxiety (particularly, separation anxiety)
    - ii. Emotional lability (extreme mood swings) and/or depression
    - iii. Irritability, aggression and/or severely oppositional behaviors
    - iv. Behavioral (developmental) regression (examples, talking baby talk, throwing temper tantrums, etc.)
    - v. Deterioration in school performance
    - vi. Sensory or motor abnormalities

- vii. Somatic signs and symptoms, including sleep disturbances, bedwetting or urinary frequency
3. Signed informed consent of patient's legal representative(s)/guardians(s). If patients are old enough to understand the risks and benefits of the study (as determined by each institution), they should provide written assent/consent.
4. Legal representative(s)/guardians(s) must be capable of understanding and complying with the relevant aspects of the study protocol.

Patients who will additionally meet the following optional inclusion criteria will be identified as PANDAS patients:

1. An episodic (relapsing-remitting) course of symptom severity.
2. Temporal association between symptoms onset or exacerbation and GAS infections (positive throat culture and/or anti-GAS antibody titers).

#### **4.1.2 Exclusion Criteria**

Patients who meet any of the following criteria are not eligible for the study:

1. Onset of current PANS episode more than 12 months prior to first IMP treatment.
2. a. In patients with relapsing episodes: Onset of initial PANS episode more than 24 months prior to first IMP treatment  
b. In patients with relapsing episodes: Absence of significant improvement and stabilization between the episodes according to investigator's judgment.
3. Contraindications to receiving IVIG, including:
  - a. History of severe hypersensitivity, e.g. anaphylaxis or severe systemic response, to immunoglobulin, blood or plasma-derived products, or any component of Panzyga.
  - b. IgA deficiency with antibodies to IgA (<7 mg/dL).
  - c. Hyperviscosity syndromes or known or suspected hypercoagulable conditions as inferred from clinical history, which can increase risks of thrombosis associated with IVIG administration.
  - d. History of arterial or venous thrombotic or TEEs within the last year prior to Baseline. History of acquired or inherited thrombophilia any time prior to Baseline.
  - e. Need for live virus vaccine within three months after receiving study drug.
  - f. Renal dysfunction (creatinine > 120 µmol/L or 1.36 mg/dL), history of renal dysfunction, or known risk factor for renal dysfunction (chronic renal insufficiency, diabetes mellitus, taking known nephrotoxic medication). For Italy, estimated glomerular filtration rate (eGFR) needs to be calculated with the 2009 Schwartz equation (eGFR = k \* height/Serum creatinine (SCr), where k is 0.413) [2]. eGFR must not be below 30.

4. Severely restricted food intake likely to require parenteral nutrition, and <5th percentile BMI-for-age (BMI Percentile Calculator for Child and Teen based on Centers for Disease Control and Prevention growth charts for children and teens ages 2 through 19 years).
5. Body mass index  $\geq 40 \text{ kg/m}^2$ .
6. Presence of symptoms consistent with autism or schizophrenia, bipolar disorder, or other psychotic disorder (unless psychotic symptoms have onset coincident with PANS).
7. Presence of serious or unstable medical illness, psychiatric (e.g. high suicide risk) or behavioral symptoms that would make participation unsafe or study procedures too difficult to tolerate.
8. Treatment with systemic corticosteroids within eight weeks before randomization.
9. Treatment with NSAIDs within five days before randomization.
10. Treatment with melatonin within one week before randomization.
11. History of rheumatic fever, including SC (neurological manifestation).
12. Past treatment of neuropsychiatric symptoms with immunomodulatory therapy (such as IVIG, rituximab or mycophenolate mofetil) or plasmapheresis.
13. Initiation of CBT within eight weeks before randomization.
14. Start of treatment or change in dosing with SSRIs within eight weeks before randomization.
15. Treatment with alpha-2 agonists or antipsychotics within eight weeks before randomization.
16. Start of treatment or change in dosing with stimulants (Methylphenidate, Amphetamine and similar products) for ADHD within four weeks prior to randomization.
17. Active use of THC-containing agents within four weeks prior to enrollment or during the trial. Use of CBD/CBM-containing agents without THC is allowed if started more than eight weeks before enrollment in a stable dose/frequency.
18. Use of antibiotics or antiviral drugs at therapeutic dose within one week before randomization. Use of antibiotics at a prophylactic dose is allowed if started at least four weeks before randomization (Section 4.2).
19. Severe liver disease (ALT three times above normal value).
20. Known hepatitis B, hepatitis C or HIV infection as per patient medical history.
21. Cardiac insufficiency (NYHA classification III-IV), cardiomyopathy, significant cardiac dysrhythmia requiring treatment.
22. Medical conditions with symptoms and effects that could alter protein catabolism and/or IgG utilization (e.g. protein-losing enteropathies, nephrotic syndrome).

23. Pregnant and/or lactating women

24. Female patients of childbearing potential unwilling to use a protocol-required method of contraception (as per protocol Section 7.3.9 b) from Screening throughout the study treatment period and for four weeks following the last dose of study drug. A woman of childbearing potential (WOCBP) is defined as a fertile woman or adolescent, from the beginning of menstruation, unless permanently sterile.

25. Participation in another interventional clinical trial that is either blinded or involves an investigational (not approved) product within three months before Baseline or during the course of the clinical study. Participation in observational clinical trials or open-label trials involving an approved product may be permitted after consultation with the medical monitor.

